3.4 Recruitment and Screening

Individuals attending the clinic for PrEP assessment are either referred from other health care providers or referred by themselves (self-referral).

Those who have commenced PrEP elsewhere (abroad, purchased themselves, another provider) and attend for "PrEP follow-up" either at Olafiaklinikken or a corresponding venereological clinic/study site in Norway, may also be included in the study.

Eligible subjects will have the study explained to them, and will receive the written informed consent form (ICF). After having had the time to review the nature of the study, they will have the opportunity to ask questions to the investigating team. If the subject agrees to participate, they will be asked to sign and date one original written informed consent form (ICF). The subject will then receive a copy of the signed and dated patient information/informed consent form. The original signed ICF will be filed in the Investigator Site File (ISF). The PIS will contain site contact information in case of any questions or medical emergency.

Newly diagnosed HIV positive individuals referred to the out-patient clinic of the Dept. of Infectious Diseases, OUS, will be invited to participate as controls. The inclusion and exclusion criteria for the control group aim at including newly infected individuals (< 12 months) residing in a country for > 6 months where PrEP might have been available, and excluding individuals infected long time ago in a country where PrEP was inaccessible; i.e. mostly countries with high HIV-prevalence outside the EU/EFTA-region, North America and Australia/New Zealand. They will be presented with the same consent form and questionnaire on sexual and psychological health prior to the HIV diagnosis.

Any written information given to potential subjects will be submitted to, and approved by, the Ethics Committee(s) prior to implementation.

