2 OBJECTIVES

This study is designed to evaluate implementation of PrEP treatment as a part of the general HIV preventive program in Norway. The target groups are mainly MSM and transgender persons at high risk of HIV infection, as well as other subjects at risk of HIV infection due to their sexual practices.

Objectives include assessment of the following:

- Assess the impact of PrEP on the sexual and psychological health of PrEP users
- Incidence of sexually transmitted infections (STIs) in PrEP users compared to those not taking PrEP
- Assessment of drug compliance
- Incidence of HIV seroconversion despite PrEP
- Frequency and development of drug resistance in subjects who HIV-seroconvert (if any)

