3 POPULATION

3.1 Inclusion Criteria

In order to participate in the PrEP arm of this study the subjects must meet all of the following inclusion criteria:

1. Male, female or transgender persons aged ≥ 18 years who are offered or have started PrEP in routine clinical practice, and 2, 3, 4, 5, 6 or 7 (below).
2. Men who have sex with men (MSM) and transgender persons;
 - a. who have had unprotected anal sex with two or more partners during the last six months and/or
 - b. who have had bacterial sexually transmittable infection(s) during the last twelve months and/or
 - c. who have used post-exposure prophylaxis(PEP) during the last twelve months and/or
 - d. who use recreational drugs when having sex
3. Indication for PrEP is present according to the assessment of the health care provider
4. Men and women who are at high risk of HIV according to their sexual practices
5. HIV-negative partner of a HIV-positive person not yet virologically suppressed by antiretroviral therapy (ART)
6. Sex workers with inconsistent condom use
7. Persons with inconsistent condom use with sexual partners in / from countries with a high prevalence of HIV (COHP)

Subjects who are included in the PrEP arm will act as their own controls regarding possible changes in psychological and sexual health. At the screening visit they will complete questionnaire requesting information related to last 6 months prior to study start. Individuals who seroconvert during the observational period will be transferred to the out-patient clinic for Infectious Diseases as is already standard of care.

Patients diagnosed with HIV in general clinical practice and referred to the out-patient clinic at the Dept. of Infectious Diseases, OUS, will be asked to act as controls to assess their past psychological and sexual health. They will be asked to sign the consent form and answer the same questionnaire as those in the PrEP arm but not followed further in this study.

Frequency of STI reported to the National Institute of Public Health (MSIS) will be compared with the frequency of STIs in the study cohort.

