3.3 Control Group

Subject to be included in the control group:

1. Enrolled patients will be regarded as their own control when it comes to their sexual health and quality of life reported for period prior to inclusion in the study.
2. Subjects newly diagnosed with HIV in general clinical practice and referred to the out-patient clinic at the Dept. of Infectious Diseases, OUS, who meet the following inclusion and exclusion criteria:
 - a. Inclusion criteria in the control group:
 - i. Confirmed positive HIV-test, AND
 1. Confirmed negative HIV-test < 12 months ago, OR
 2. Self-reported assumed time of infection < 12 months ago, AND
 - ii. Resident for > 6 months in a country of one of the following regions (EU/EFTA, North America or Australia/New Zealand) at the time of confirmed or assumed infection.
 - b. Exclusion criteria in the control group:
 - i. Confirmed positive HIV-test > 12 months ago, OR
 - ii. Self-reported assumes time of infection > 12 months ago.
3. Frequency of STI reported to the National Institute of Public Health (MSIS) will be compared with the frequency of STIs in the study cohort.

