3.5 Subject Withdrawal

In accordance with the Declaration of Helsinki, the Investigator must explain to the subject that they have the right to withdraw from the study at any time, and that this will in no way prejudice their future treatment. The reason for any kind of withdrawal should be recorded on the appropriate CRF.

If a subject is proven HIV positive when using PrEP, the treatment should be stopped immediately to prevent development of resistance, registered as a PrEP failure, and referred to the Dept. of Infectious Diseases for regular follow-up of their HIV infection and checked for resistance to tenofovir disoproxil fumarate and emtricitabine (as is already standard clinical practice).

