### **3.3 Control Group**

Subject to be included in the control group:

1. Enrolled patients will be regarded as their own control when it comes to their sexual health and quality of life reported for period prior to inclusion in the study.
2. Subjects diagnosed with HIV in general clinical practice and referred to the out-patient clinic at the Dept. of Infectious Diseases, OUS.
3. Frequency of STI reported to the National Institute of Public Health (MSIS) will be compared with the frequency of STIs in the study cohort.

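### The criteria for HIV-diagnosed controls do not address PrEP use, so people infected during or soon after PrEP can enter the group compared with the PrEP arm

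*Protocol*

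**What the plan says.** On recruitment, Protocol 3.4 states: "Newly diagnosed HIV positive individuals referred to the out-patient clinic of the Dept. of Infectious Diseases, OUS, will be invited to participate as controls".

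Protocol 3.3, item 2, defines this control group as "Subjects newly diagnosed with HIV in general clinical practice and referred to the out-patient clinic at the Dept. of Infectious Diseases, OUS, who meet" a short list of criteria.

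- **Inclusion:** a confirmed positive test, together with either "Confirmed negative HIV-test < 12 months ago, OR" or a self-reported infection within the same window, and more than six months' residence in the EU/EFTA, North America or Australia/New Zealand.
- **Exclusion:** two items only, "Confirmed positive HIV-test > 12 months ago, OR" and a self-reported infection more than 12 months ago.

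Protocol 3.4 explains that these criteria aim at recently infected people living where PrEP could have been obtained. The same section lets people join the PrEP arm who started PrEP abroad, bought it themselves or got it from another provider.

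For PrEP-arm participants who become infected, Protocol 3.1 states: "Individuals who seroconvert during the observational period will be transferred to the out-patient clinic for Infectious Diseases as is already standard of care". Protocol 3.5 adds that such a person is "registered as a PrEP failure, and referred to the Dept. of Infectious Diseases for regular follow-up of their HIV infection".

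The SAP's section 3.3 defines the same controls only as "Subjects diagnosed with HIV in general clinical practice and referred to the out-patient clinic at the Dept. of Infectious Diseases, OUS", without recency or residence criteria. Its section 3.4 adds that they are newly diagnosed.

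Under Protocol 3.1 these controls complete the PrEP arm's questionnaire once, about their past psychological and sexual health, and are not followed. Sections 7.2 to 7.4 contain no rule for a control who has used PrEP.

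**The concern.** The plan sets a PrEP arm beside a control group, so a reader will take the difference between them as PrEP users against people who acquired HIV without it. The criteria do not secure that reading. They select on possible access to PrEP and on recent infection, and leave use of PrEP open. As PrEP becomes easier to obtain, some newly infected people will have been using it or have recently stopped.

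Two things are at stake. First, the control group has no clear identity: it may mix people who never took PrEP, people who stopped, and people infected while taking it. Second, the controls answer one questionnaire and are not seen again in the study, so a PrEP history not asked for at that point may be unrecoverable when the data are analysed.

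**Working it through.** **Step 1. Two hypothetical people read against each control condition in Protocol 3.3.** A was infected during or soon after PrEP obtained outside the study. B is an Oslo PrEP-arm participant who seroconverts.

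| Condition | A | B |
|---|---|---|
| Confirmed positive test | Met | Met |
| Negative test or assumed infection within 12 months | Met if infection is recent | Met: tested about every 3 months (Protocol 4.1, Table 1) |
| More than 6 months' residence in a listed region | Normally met | Normally met |
| Diagnosed in general clinical practice | Met | Not settled by the text |
| Referred to the OUS Infectious Diseases clinic | Met if referred there | Likely for Oslo; Protocol 3.1 and 3.5 do not name the hospital |
| Either 12-month exclusion | Does not apply | Does not apply |
| Any condition on PrEP use | None stated | None stated |

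A is eligible without qualification. B is eligible unless the general-practice condition is read as shutting out study participants. The general exclusion of HIV-positive subjects in Protocol 3.2 cannot serve as the filter: read literally, it would bar every HIV-diagnosed control.

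**Step 2. How many people like B?** The plan gives no figure to reproduce; its sample size entry is not applicable. The following is for scale only.

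Inputs from the protocol's introduction, both background figures and not estimates for this cohort: HIV incidence of 3 per 100 person-years in populations identified for PrEP, and 86% protection.

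Assumptions: 300 to 1000 PrEP users. Protocol 4.2 closes inclusion at the end of 2018. If that also applies to controls and accrual is uniform over 1 to 2 years, mean follow-up by closure is 0.5 to 1 year.

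- Rate on PrEP: 3 × (1 − 0.86) = 0.42 per 100 person-years.
- By the end of 2018, low: 300 × 0.5 = 150 person-years; 150 × 0.0042 = 0.6.
- By the end of 2018, high: 1000 × 1 = 1000 person-years; 1000 × 0.0042 = 4.2.
- Full 24 months, low: 300 × 2 = 600 person-years; 600 × 0.0042 = 2.5.
- Full 24 months, high: 1000 × 2 = 2000 person-years; 2000 × 0.0042 = 8.4.

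These are upper limits on entry to the control group, because they suppose that every seroconverter is referred to OUS, invited and consents. They scale directly with the rate: at an assumed 50% protection the rate is 3 × 0.5 = 1.5, and each count is multiplied by 1.5 / 0.42 = 3.6.

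**Step 3. As a share of the control group.** The documents give no number of controls. With an assumed 60 other controls, and the entrants counted in the denominator:

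- By the end of 2018: 0.6 / 60.6 = 1.0% to 4.2 / 64.2 = 6.5%.
- Full 24 months: 2.5 / 62.5 = 4.0% to 8.4 / 68.4 = 12.3%.

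**Step 4. How many people like A?** The documents give no basis for an estimate.

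**The case against.** The strongest reply is that study seroconverters are already kept out. Protocol 3.1 deals with them in one paragraph, as a transfer for standard care, and with controls in the next, as people diagnosed in general clinical practice. Protocol 3.5 refers them for follow-up of their infection, not for recruitment. That is a plausible reading and may be the intended one. It is not decisive, because Protocol 3.1 enrols people given PrEP in routine practice, so diagnosis at a study clinic could count as general practice too. It also does nothing about PrEP taken outside the study.

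A second reply is that no section says these controls represent people without PrEP. That is correct. The reading is an inference from the contrast between a PrEP arm and controls. If PrEP-exposed controls are wanted, the plan should say so and report them as such.

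A third is that the questionnaire may already ask about PrEP. It may; its items cannot be read from the documents. Even so, no stated rule uses the answer.

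The objectives include "Incidence of sexually transmitted infections (STIs) in PrEP users compared to those not taking PrEP", and a reader might infer that this comparison is compromised. The documents do not support that. Sections 3.1 and 3.3 assign the STI comparison to national surveillance data (MSIS), and controls who answer one questionnaire cannot supply incidence over follow-up.

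**Conclusion.** The gap is real. As written, the criteria admit PrEP-exposed people to the group compared with the PrEP arm on past sexual and psychological health, and they do not plainly keep out the study's own seroconverters, at least in Oslo. It is worth correcting because it is cheap to close and PrEP history may be lost if it is not asked at consent.

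The size is probably small: about 0.6 to 4 study seroconverters by the end of 2018, or 2.5 to 8 over a full 24 months. This rests on two background figures and assumed cohort size and accrual. PrEP users from outside the study would add an unknown number.

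Three stronger readings are tempting but unsupported:

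- **That the same person will certainly be counted in both groups.** This requires setting aside the general-practice condition.
- **That the difference is pulled towards zero.** People selected by seroconversion may differ from other PrEP users in risk or adherence, so the direction is unknown. Nor is a significance test affected by overlap, since section 7.3 plans descriptive statistics only.
- **That a quarter or more of the controls could be the study's own PrEP failures.** That needs the largest assumed cohort set against the smallest assumed control group, a full 24 months of failures, and complete referral and consent.

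**What to change.** 1. In Protocol 3.3, item 2b, add an exclusion from the control group: *enrolled in the PrEP arm of this study*.
2. Ask every HIV-diagnosed control at consent about PrEP use from any source in the 12 months before the first positive HIV test, and record the answer.
3. State in section 7 that the main comparison uses controls with no PrEP use in that period, and that PrEP-exposed controls are reported separately.
4. Bring SAP section 3.3 into line with Protocol 3.3.

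The cost is one extra question and slightly fewer controls in the main comparison. Exposed controls are still described, so apart from PrEP-arm participants nobody is turned away. Clinical care is unchanged.

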3.5 Subject Withdrawal

In accordance with the Declaration of Helsinki, the Investigator must explain to the subject that they have the right to withdraw from the study at any time, and that this will in no way prejudice their future treatment. The reason for any kind of withdrawal should be recorded on the appropriate CRF.

If a subject is proven HIV positive when using PrEP, the treatment should be stopped immediately to prevent development of resistance, registered as a PrEP failure, and referred to the Dept. of Infectious Diseases for regular follow-up of their HIV infection and checked for resistance to tenofovir disoproxil fumarate and emtricitabine (as is already standard clinical practice).

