		
alcohol use.
 
Subject will be screened for the following STIs during the enrolment visit: HIV, syphilis, hepatitis A/B/C, Chlamydia trachomatis, Neisseria gonorrhoea, and Mycoplasma genitalium.
 
Participants will be asked to return approximately one week later to discuss their HIV result and whether they wish to proceed with initiation of PrEP.
 
The decision regarding initiation of continuous or intermittent PrEP is based on a discussion with the subject and study team (doctor/nurse), subjects' personal preference, medical considerations and whether the expected use will surpass more than 15-20 tablets of FTC/TDF per month.
 
HIV testing will be repeated at 2, 4 and 8 weeks from the most recent high risk exposure (for HIV acquisition) prior to initiation of PrEP. Thereafter participants are requested to visit the clinic every 3 months from PrEP initiation (for the next 24 months) for HIV & STI testing, evaluation of compliance (blood test for drug monitoring in continuous PrEP arm, drug diaries in both continuous and intermittent PrEP arms), assessment of clinical and/or biochemical adverse reactions and quality of life and sexual behaviour assessment. Subjects will be asked to answer the same questions regarding sexual behaviour and quality of life at follow up visits as at inclusion study visit.

Statistics	Sample size	Not applicable
	Methods	Categorical variables will be described by means of absolute and relative frequencies, while continuous variables by means of mean, standard deviation, quartiles, min and max.

LIST OF ABBREVIATIONS

AE	Adverse Event
ART	Anti retroviral therapy
COHP	Country of high prevalence of HIV
CRA	Clinical Research Associate
CRF	Case Report Form
CSR	Clinical Study Report
CT	Chlamydia trachomatis
DM	Data Manager
EC	Ethics Committee
eCRF	Electronic Case Report Form
EDC	Electronic Data Capture
EMA	The European Medicines Agency
GCP	Good Clinical Practice
HIV	Human Immunodeficiency Virus
ICF	Informed Consent Form
ICH	International Conference on Harmonisation
IMP	Investigational Medicinal Product
ISF	Investigator Site File
ITT	Intention-To-Treat
MG	Mycoplasma genitalium
MSM	Men who have sex with men
NG	Neisseria gonorrhoea
PI	Principal Investigator
PIS	Patient Information Sheet
PrEP	Pre-Exposure Prophylaxis
SAE	Serious Adverse Event
SD	Standard Deviation
SDV	Source Data Verification
SUSAR	Suspected Unexpected Serious Adverse Reaction
STI	Sexually Transmitted Infections

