1.1 Aim of Present Study

The main objective of this study is to monitor the impact of PrEP on the subject's psychological and sexual health. It is also important to monitor the adherence to PrEP, development of drug resistance (in the case of undetected HIV infection at initiation of PrEP), frequency of other STIs, changes in sexual behaviour, recreational drug use and quality of life. PrEP has proven to be effective in reducing the sexual acquisition of HIV, however this requires that the medication is taken as prescribed, whilst the subject is exposed to high risk of infection.

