4 TREATMENT PROCEDURES

4.1 Study plan

The observation will begin after the subjects have signed the informed consent form. PrEP treatment should then be initiated when the HIV antibody/antigen test (4th generation test) taken at the first visit is confirmed negative.

However, the window period to rule out HIV infection is 12 weeks. It is not desirable that participants are undergoing HIV seroconversion when they commence PrEP, however the study population is per definition at high-risk for HIV acquisition. It is likely that the majority of the participants will not be in a position to abstain from sex or use condoms effectively for a 12 week period. Therefore it is NOT recommended to delay PrEP pending a negative HIV test results 12 weeks from the last high risk exposure. International and national guidelines do not recommend delaying PrEP initiation in this high risk group for HIV acquisition. Per definition, those in need for PrEP are at high risk for HIV acquisition justifying PrEP initiation even at first visit.

For those who have had high risk exposure within 14 days prior to screening, a HIV-DNA provirus test should be requested and the serum test for HIV should be repeated at 2 weeks, 4 weeks and 8 weeks and 12 weeks from the day they commenced PrEP.

Subjects that have already commenced PrEP treatment can be included in the study. These subjects will be requested to consent to collection of historical medical information from the date when the PrEP treatment was initiated.

Follow-up visits are according to clinical practice, clinical judgement and standard patient management described in SmPC. For those outside the window period for HIV infection a standard visit at 4 weeks and 12 weeks post initiation of PrEP and thereafter every 3 months during the PrEP treatment for 24 months. Where clinically indicated the subject may attend the clinic between 3 months' follow-up visits. Data from these visits will be collected as Extra Clinical Visits.

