4.2 Variables

Subjects will be treated according to local prescribing information and clinical judgement and assessments performed according to site clinical practice. The inclusion period will last from final approval from The Regional Ethical Committee and until end of 2018.

Data on demographics, sexual health including sexual behaviour, HIV infection status, STIs, compliance and recreational drug use will be collected at the baseline visit, 3 months' follow-up visits, end of study visit and relevant extra visits. HIV-tests will also be taken at weeks 2, 4 and 8 in order to identify people in the seroconversion phase at inclusion to reduce risk of development of drug resistance. For subjects at particular high risk for HIV infection prior to PrEP treatment, HIV-DNA provirus testing will be assessed at the first visit according to the doctor's clinical judgement. As a measure of adherence blood samples will be drawn and the tenofovir disoproxil fumarate (TDF) concentration in plasma will be measured as well as a self-reported drug protocol.

Investigators are asked to report the requested data in the electronic Case Report Form (eCRF).

Table 1 Data collection and visit structure

Study Visits ¹	Visit 0 (evaluation)	Visit 1(start of treatment)	Visit 2 (week 2)	Visit 3 (week 4)	Visit 4 (week 8)	Follow-up visits (approx. every 3 months)	Extra visits	End of study visit (24 months after start of treatment)
Clinic visits	x			x		x ¹	x	x
Informed consent	X							
Assess eligibility criteria	x	x						
Demography	X							
HIV test ²	x		x	x	x	x	x ³	x
HIV-DNA provirus ⁴	x ⁴	x ⁴						
History of STI	x							
STI screening	x					x	x ³	x
Bloodsample for TFV-PD plasma concentration				x		x ⁵	x ^{3,5}	x ⁵
Questionnaire sexual behaviour (start of treatment)	x					x		x
Questionnaire sexual behaviour (follow-up)	x					x		x
Compliance				x		x	x	x
Adverse events				x		x	x	x
Subject diary				x		x		x

¹ clinic visits to be schedule to fit with PrEP treatment guidelines and local clinical practice. At each visit assessments as indicated in table should be captured in the database if they are conducted.

² If a subject is infected with HIV during PrEP treatment resistance of the HIV virus for emtricitabine and tenofovir disoproxil fumarate should be checked.

³ If clinically indicated

⁴ If high risk sexual contact within the last 14 days

⁵ only applicable for subject on continuous PrEP treatment

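### Section 3.5 registers every HIV positive found on PrEP as a PrEP failure, including infections already present at PrEP start that the early tests are meant to find

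*Protocol*

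**What the plan says.** Section 3.5 of the protocol (repeated in 3.5 of the SAP file) has one rule for a subject who is "proven HIV positive when using PrEP, the treatment should be stopped immediately to prevent development of resistance, registered as a PrEP failure". The same sentence covers referral and resistance testing. It sets no condition on when the infection was acquired.

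Section 4.1 says of the test that gates PrEP start: "However, the window period to rule out HIV infection is 12 weeks". It adds that "It is not desirable that participants are undergoing HIV seroconversion when they commence PrEP", but advises sites not to wait out the window and accepts a start even at the first visit. Section 4.2 then places HIV tests at weeks 2, 4 and 8 "in order to identify people in the seroconversion phase at inclusion to reduce risk of development of drug resistance".

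Before dosing, the only planned test beyond antibody/antigen is HIV-DNA provirus. Table 1 puts it at Visit 0 and Visit 1, with the footnote "If high risk sexual contact within the last 14 days". Section 4.1 uses the same 14-day trigger; the text of 4.2 leaves the test to clinical judgement.

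The fourth objective in section 2 is "Incidence of HIV seroconversion despite PrEP". Section 1.1 names infection undetected at PrEP start as a resistance situation of interest. Section 7 defines no seroconversion count, and 7.2 removes only subjects who fail the inclusion criteria.

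**The concern.** An infection acquired before the first dose cannot be a failure of PrEP to prevent it. The protocol expects such infections and tests for them, then gives them the same label as a breakthrough infection.

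Two results are at stake. The first is the rate of seroconversion on PrEP. A subject who is negative at Visit 0 and positive at week 4 fits the words of that objective whether infection came before or after the first dose, so a count taken from the label, or from those words, can be too high. The second is resistance. Resistance that emerges when an unrecognised infection is exposed to two drugs is a different finding from resistance in a breakthrough infection, and one label merges them. If no rule is set in advance, early positives would be classified after the cases are known.

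**Working it through.** The documents give no sample size, expected event count or seroconversion rate, so there is no plan figure to reproduce. The main check sets the sections side by side.

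1. **Can an infected subject start PrEP?** Yes. The gating test has a stated 12-week window and 4.1 advises against waiting. The Protocol outline also has participants return about one week after Visit 0, and Table 1 shows no antibody/antigen test at Visit 1.
2. **Does the protocol expect to find such subjects?** Yes. This is the stated purpose of the week 2, 4 and 8 tests.
3. **How is such a subject registered?** As a PrEP failure under 3.5, because the positive result arrives while PrEP is in use.
4. **Does another section correct this?** No. HIV positivity is exclusion criterion 1, but 7.2 removes only inclusion-criteria failures, and nothing says how infection at baseline would be established later.
5. **Who has a pre-dose result that could separate the two types?** Those with high-risk contact in the 14 days before Visit 0 or Visit 1. The Visit 1 test also reaches high-risk exposures in the week between the visits, and someone infected earlier who has a later high-risk contact is tested too. The remaining group is those last exposed 15 days to 12 weeks earlier whose infection the Visit 0 test missed, plus anyone not tested in practice.
6. **Do dates help?** Partly. Start date and date of first positive are planned data, but no cut-off is written. The documents also differ on the early tests: 4.1 ties the 2, 4, 8 and 12-week series to exposure within 14 days and counts from PrEP start, the outline counts from the last exposure, and Table 1 shows weeks 2, 4 and 8 for everyone.

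**Range for the rate.** Let w be the weeks' worth of pre-dose infections that reach the first dose undetected by any planned test. The documents do not give w, so it is an assumption, running from 0 to 12. Other inputs:

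- 86% protection (section 1);
- 3 infections per 100 person-years without PrEP, a guideline figure cited in section 1 and not an estimate for this cohort;
- 24 months of follow-up (5.4);
- assumed: equal exposure before and after start, and all subjects new starters.

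Infections acquired on PrEP per 100 starters: 3 × 0.14 × 2 = 0.84, a rate of 0.84/2 = 0.42 per 100 person-years.

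Entry infections per 100 starters: 3 × w/52.

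Rate if all are counted as failures: (0.84 + 3w/52)/2.

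- w = 0: 0.42
- w = 2: (0.84 + 0.115)/2 = 0.478
- w = 4: (0.84 + 0.231)/2 = 0.535
- w = 12: (0.84 + 0.692)/2 = 0.766

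If half the cohort were already on PrEP at enrolment, the excess halves; at w = 12 the rate is 0.42 + 0.346/2 = 0.593. The value at w = 12 supposes that every infection in the stated window is missed and that no provirus test finds any. It is a limit under these assumptions, not an estimate.

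**The case against.** The strongest reply has four parts.

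**Planned testing already covers much of the risk.** Provirus testing at both Visit 0 and Visit 1 reaches the most recent high-risk exposures, where an antibody/antigen test would be expected to be weakest. This stands. A reader might infer from the 12-week window that most positives in the first 12 weeks would be entry infections. The documents do not support that: any such share has to assume how many infections escape the planned tests, and no figure is given.

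**The label is not stated to be the numerator.** Section 3.5 concerns withdrawal and clinical management, no section says its registration feeds the seroconversion objective, and 7.1 defers to a separate SAP that was not supplied (the SAP file is a near copy of the protocol). This also stands, so upward bias is a possibility and not an established result. But no other definition appears, and the objective's own words take in the same cases.

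**The study is descriptive.** Sample size is given as not applicable and section 7 plans summaries only. A reader might infer that one or two misclassified cases would reverse a conclusion. With no hypothesis, threshold or expected count in the documents, that cannot be shown.

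**It can be handled at analysis.** Largely true. Early positives can be set apart by date and the rate given both ways. A reader might infer that a stored pre-dose sample from everyone is essential; it would sharpen the split, but a bounded answer does not need it.

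None of this removes the mismatch between 3.5 and 4.2.

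**Conclusion.** The point holds in limited form. As written, 3.5 assigns infections that predate PrEP to PrEP failure, and no other section corrects it. The seroconversion rate can be biased upward, and two resistance situations are mixed.

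The size is unknown. It depends on how many infections present at start escape both the antibody/antigen test and the conditional provirus test, on how fully that test is done, and on the proportion of new starters. The range in the working shows direction and limits under stated assumptions and should not be quoted as an expected bias. The conclusion itself rests on the wording of 3.5, 4.1, 4.2 and Table 1, and on no separate SAP having been available that settles the matter.

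**What to change.** In 3.5, keep the instructions to stop PrEP, refer and test for resistance. Replace the single label with three classes:

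- **(a) Infected at entry:** pre-dose HIV-DNA positive.
- **(b) Indeterminate:** a new starter, first positive by week 12 after PrEP start, not shown to be infected at entry.
- **(c) Acquired on PrEP:** first positive after week 12, following earlier negative tests.

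A new starter who is first positive after week 12 but has no negative test late enough to close the window is best placed in (b).

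Report the seroconversion objective using (c), and again using (b) plus (c), over the same person-time; leave (a) out of both. The first figure omits any true breakthrough in the first 12 weeks and the second may include entry infections, so the two bracket the answer. Report resistance results separately by class. State that a subject already taking PrEP who is positive at Visit 0 is not counted as an on-study seroconversion. Make the same change in the SAP.

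The cost is one eCRF field, a few lines of text, and a rate reported as a range. All inputs (start date, test dates, provirus results) are already planned. Storing a pre-dose sample from every new starter is optional; it would narrow (b), but adds site work and would probably need changes to consent and the protocol.
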